## 1. List of Abbreviations and Acronyms

ACTU	AIDS Clinical Trials Unit
AE	adverse event
AIDS	Acquired Immunodeficiency Syndrome
aPTT	activated partial thromboplastin time
ALT	alanine aminotransferase
AST	aspartate aminotransferase
AUC	area under the time vs. concentration curve
BP	blood pressure
CBC	complete blood count
CPAC	Clinical Pharmacology Analytical Chemistry
CPT	cell preparation tube
CRF	case report form
CT	Chlamydia (Chlamydia trachomatis)
CTRC	Clinical and Translational Research Center
DAIDS	Division of AIDS
DBS	dried blood spots
DNA	deoxyribonucleic acid
EAE	expedited adverse event (reporting)
EC	ethics committee
eCcr	estimated calculated creatinine clearance
FDA	(United States) Food and Drug Administration
FHT	feminizing hormone therapy
FTC	emtricitabine
FTC-TP	emtricitabine triphosphate
GC	gonorrhea ( Neisseria Gonorrhoeae )
GCP	good clinical practices
GI	gastrointestinal
HepBsAg	hepatitis B surface antigen
Hep C Ab	hepatitis C antibody
HIV	Human Immunodeficiency Virus

HR	heart rate
ICH	International Conference on Harmonisation
IDS	investigational drug service
IRB	institutional review board
IUD	intrauterine device
LLN	lower limit of normal
LLOQ	lower limit of quantification
MRN	medical record number
MSM	men who have sex with men
NC TraCS	North Carolina Translational and Clinical Sciences Institute
NIAID	(United States) National Institute of Allergy and Infectious Diseases
NIH	(United States) National Institutes of Health
NRTI	nucleos(t)ide reverse transcriptase inhibitor
OHRP	Office for Human Research Protections
PD	pharmacodynamics
PI	principal investigator
PK	pharmacokinetics
PrEP	pre-exposure prophylaxis
PSRT	Protocol Safety Review Team
PT	prothrombin test
QA	quality assurance
QC	quality control
RPR	rapid plasma reagin test for syphilis
RR	respiration rate
SAE	serious adverse event
SOP	standard operating procedures
SST	serum separator tube
STI	sexually transmitted infection
TDF	tenofovir disoproxil fumarate

TDF/FTC	Truvada® (tenofovir disoproxil fumarate and emtricitabine in fixed dose combination)
TFV	tenofovir
TFV-DP	tenofovir diphosphate
TGW	transgender women
TraCS	The North Carolina Translational and Clinical Sciences Institute
ULN	upper limit of normal
UNC	University of North Carolina

2. List of Figures and Tables

Figure 1. Sampling Schema Pictorial.....	11
Figure 2. Theoretical Framework .....	16
Figure 3. Truvada® Identification .....	25
Figure 4. Power Determination.....	39

## 3. Terminology for Study Drug

Abbreviation	Compound name	Comments
TDF	Tenofovir disoproxil fumarate	This is the inactive, oral formulation of tenofovir (trade name: Viread). The ester form enhances oral absorption and bioavailability. TDF is rapidly metabolized after dosing to the de-esterified pro-drug, tenofovir (TFV), which is also inactive.
TFV	Tenofovir	This is the inactive, de-esterified form of TDF. This is the form of the drug that is measured in serum, blood, other body fluids, and tissue samples.
TFV-DP	Tenofovir diphosphate	This is the active, phosphorylated form of tenofovir that is generated in cells. This is the form of the drug that is measured in cells (e.g., PBMCs). It is rapidly dephosphorylated to the inactive form outside of cells, and has a very short half-life outside of cells in tissue.
FTC	Emtricitabine	This antiretroviral drug is co-formulated with TDF in Truvada® (TDF/FTC). FTC is an inactive pro-drug that is activated in cells by phosphorylation. This is the form of emtricitabine that is measured in serum, blood, other body fluids, and tissue samples.
FTC-TP	Emtricitabine triphosphate	This is the active, phosphorylated form of FTC that is generated in cells. This is the form of the drug that is measured in cells (e.g., PBMCs).
Truvada®	Tenofovir plus Emtricitabine	This is the co-formulated drug produced by Gilead Sciences, Inc. Each pill contains 300 mg of TDF and 200 mg of FTC.

## 5. Protocol Summary

Protocol Chair:	[name], MS
Sample Size:	10 cisgender females
Study Population:	Premenopausal healthy volunteer cisgender women between 18-49 years of age with an intact gastrointestinal tract
Study Site(s):	NC TraCS Clinical Translational Research Center at the University of North Carolina, Chapel Hill, NC USA
Study Design:	Single-center, open-label PK sampling study
Study Duration:	Women will be enrolled in the study within 42 days of screening, depending on the timing of their menstrual cycle, and then will be on active study for two weeks. A follow-up visit will occur within 14 days.
Study Products:	Truvada®
Study Regimen:	Five witnessed doses daily prior to each sampling visit
Primary Objectives:	To assess the impact of high and low in vivo estradiol exposure on PrEP nucleotide concentrations in different cellular populations of the lower GI tract
Hypothesis:	PrEP nucleotide concentrations in total rectal cells collected via cytobrush will significantly correlate with concentrations in CD4 + T cells isolated from rectal tissue biopsies regardless of in vivo estradiol exposure.
Secondary Objectives:	
To quantify the relationship between estradiol, progesterone and testosterone on PrEP nucleotide concentrations in rectal and peripheral blood mononuclear cells
 
To quantify the relationship between estradiol, progesterone and testosterone on PrEP concentrations in plasma

## 6. Overview of Study Design and Allocation Scheme

### A) Allocation and Tissue Sampling Scheme:

Figure 1. Sampling Schema Pictorial

## B) Study Procedure Time and Event:

Activity ↓	Screen (-42 to 0 Days)	Enrollment /Dose 1	Dosing Days	Sampling Visit 1	Dosing Days	Sampling Visit 2	Follow-up (Within 14 days)
Eligibility	X	X					
Informed Consent	X						
Review of Medical History	X	X					
History of Menses	X						
Vital Signs a	X			X		X	X
Complete Physical Examination	X						
Targeted Physical Examination				X		X	X
Virology Tests b	X						X
Pregnancy Test c	X	X		X		X	X
STD Tests d	X						
Urine Drug Test	X						
Safety Labs e	X	X					X
Medication Dosing f		X	X		X		
Blood Sampling				X		X	
Rectal Cell Collection by cytobrush				X		X	
Rectal Tissue Biopsy				X		X	
Adverse Event Assessment		X		X		X	X

- a. Vital signs include: blood pressure, pulse, respiratory rate, temperature, and weight. Height should be documented at the screening visit.
- b. Virology tests will include HIV Ag/Ab test, HbsAg, and Hepatitis C antibody at screening visit. HIV testing will be repeated at follow up, as well as anytime infection is suspected.

- c. Serum pregnancy test will be obtained at screening visit. Urine pregnancy test will be obtained at enrollment and follow up. Participants will also have urine pregnancy test prior to sampling on assigned biopsy days.
- d. Participants will be tested for the following sexually transmitted diseases: syphilis, gonorrhea, and chlamydia.
- e. Safety labs include: CBC with differential, urine drug screen, and the following serum chemistries: Na, K, Cl, CO2, BUN, SCr, glucose, Alb, total protein, AST, ALT, Alkaline phosphatase, total bilirubin. PT/INR and aPTT will be obtained at screening. CBC without differential at follow up.
- f. Member of study team will witness dose administration.

## 7. Key Roles

### 7.1 Protocol identification

**Protocol title:** Quantification of Estradiol's Impact on Nucleotides in Different Cellular Populations of the Lower Gastrointestinal Tract

### 7.2 Clinical Laboratories

#### McLendon Labs

The following samples/tests will be processed at UNC Hospitals McLendon Core Lab:

1. Urine drug screen
2. Serum pregnancy test
3. Syphilis (RPR) titer
4. HIV diagnostic testing
5. Hepatitis testing
6. Safety labs
  - a. CBC (with differential)
  - b. Coagulation tests (PT/INR and aPTT)
  - c. Serum Chemistries

#### UNC CFAR Virology, Immunology and Microbiology (VIM) Core

The following samples/tests will be processed at UNC STD-CRC Core Lab:

1. Chlamydia test
2. Gonorrhea test

Reproductive Endocrinology Laboratory

The following analyses will be performed in a core lab directed by [name] at the Keck School of Medicine of the University of Sothern California:

1. Estradiol, Progesterone, Testosterone serum concentrations

UNC CFAR Clinical Pharmacology and Analytical Chemistry (CPAC) Core

The following analyses will be performed at the CPAC lab:

1. Plasma PrEP (TFV and FTC) concentrations
2. PBMC PrEP nucleotide (TFVdp, FTCtp, dATP and dCTP) concentrations
3. Rectal tissue and total rectal cells PrEP nucleotide (TFVdp, FTCtp, dATP and dCTP) concentrations

This laboratory, directed by [name], was created to provide clinical pharmacology expertise and laboratory support to facilitate clinical and preclinical HIV/AIDS research. The Core has been CLIA certified since December 2004 and CAP certified since 2008 and participates in four proficiency testing activities per year. The Core has > 90% accuracy for all antiretrovirals tested, has been awarded certificates of excellence and is approved to perform TDM for all PIs and NNRTIs. Sample storage, processing, and HPLC methods are performed in approximately 6000 square feet of space in in the UNC Eshelman School of Pharmacy Genetic Medicine Building. This laboratory has validated analytical methods for all currently marketed antiretrovirals.

### 7.3 Data Management Center

Data management will be maintained by the research coordinator with oversight from the principle investigator. The study records will be stored in a locked filing cabinet in a locked office located at [name],

[name]. Data will be transferred by the investigators to a password protected Microsoft Access database and stored on the UNC Secure Network Attached Storage (Secure Nas) server, which is administered and maintained by UNC IT staff, and has custom port configurations (Windows firewall) which block all unused ports and limit access to open ports based on IP address. Security logging and auditing follow industry best practices. Access to the server is restricted to key personnel including investigators, and computer support staff. User access to server resources via network connection is limited via firewall configuration, IP address filtering, and encrypted user authentication protocols. Access to the study data will be further restricted via user roles. Application security for data entry will be protected using firewalling and IP address filtering. User authentication will be managed by a single-sign-on model of log in. Passwords for access to server resources are managed in a Microsoft Active Directory repository. Passwords for applications are managed via a single-sign-on (SSO) application which stores passwords using a one-way 128 bit hashing algorithm (MD5). Password policies force users to employ “strong” passwords, which use numbers, letters and special characters. Passwords must change at least every 90 days. All data will be de-identified and assigned a nonsense random unique identifier.

## 7.4 Study Operations

This study will be conducted in accordance with ICH/GCP, The Code of Federal Regulations, Office for Human Research Protections (OHRP) and FDA regulations and guidance, in addition to department Standard Operating Procedures

The Principal Investigator (PI) accepts ultimate responsibility for the quality of the data, subject safety and protocol adherence for all research conducted through the UNC NC TraCS CTRC. She also accepts responsibility for the overall functioning of the site.

[figure not shown]
The PI is responsible for oversight of activities and responsibilities delegated to other staff. All staff are to be appropriately educated in their obligations as described above and trained in the areas for which they have delegated responsibility.

## 8. Scientific Rationale

### Female steroid sex hormones modulate enzymes involved in maintaining

**PrEP nucleotide balance.** Currently only a fixed dose combination of 2 nucleos(t)ide reverse transcriptase inhibitors (NRTIs), tenofovir disoproxil fumarate (TDF) and emtricitabine (FTC), is FDA approved for HIV pre-exposure prophylaxis (PrEP). TDF and FTC are intracellularly phosphorylated to their active forms (TFVdp and FTCtp), which compete with the host cells' naturally occurring deoxynucleotides (dATP and dCTP) for incorporation into the proviral DNA strand to block reverse

Figure 2 Theoretical Framework

transcription. The female sex steroid hormone, estradiol, increases expression of 5' nucleotidase enzymes involved in maintaining intracellular nucleotide balance. Particularly, ecto-5' nucleotidase (located on the extracellular surface of the plasma membrane) catalyzes AMP to ADP, which is a precursor in the biochemical formation of dATP. Conversely, intracellularly expressed cytosolic 5' nucleotidase may dephosphorylate and deactivate PrEP's active metabolites (TFVdp and FTCtp; Figure 2).

**Female sex steroid hormones may disproportionately impact PrEP pharmacology in different cellular populations.** Previously, investigators have utilized several different sampling strategies from which to draw conclusions about PrEP pharmacology in HIV transmission sites. These surrogate measures include 1) collecting biopsies for measurement in isolated CD4+ T cells – generally considered gold standard; 2) tissue homogenization for measurement in mixed cell populations; 3) collecting swabs and cytobrush for measurement in fluid or mixed cell populations. A previous clinical study noted a predictive relationship between parent TFV measured in rectal fluids versus tissue homogenates in individuals taking oral TDF. Additionally, Yang et al. demonstrated a predictive correlation between TFVdp in mixed cell populations of homogenized rectal tissue vs CD4+ T cells isolated from rectal tissue following topical application of TFV gel. Yet the impact of estradiol on these surrogate relationships has not been well characterized. One *in vitro* study utilizing very high concentrations of TFV (1mg/ml) suggests that estradiol could disproportionately impact TFVdp formation in epithelial cells (enhanced formation) vs CD4+ T cells (diminished formation), which could confound the relationship between surrogate measures of mixed vs isolated cell populations.

**We aim to quantify estradiol's impact on PrEP nucleotide concentrations in mixed cell populations obtained via cytobrush sampling vs CD4+ T cells isolated from rectal tissue biopsies** in order to understand whether cytobrush is a valid PrEP pharmacology surrogate in people taking exogenous estradiol.

## 9. Study Objectives

### 9.1 Primary Objective:

To assess the impact of high and low *in vivo* estradiol exposure on PrEP nucleotide concentrations in different cellular populations of the lower GI tract

### 9.2 Secondary Objective(s):

To quantify the relationship between estradiol, progesterone and testosterone on PrEP nucleotide concentrations in rectal and peripheral blood mononuclear cells

To quantify the relationship between estradiol, progesterone and testosterone on PrEP concentrations in plasma

## 10. Study Design

### 10.1 Identification of Study Design

This is a single center, open-label, multi-matrix sampling study of PrEP nucleotides in mucosal tissue concentrations measured after multiple doses of Truvada® (TDF/FTC). Participants will take a single daily dose of study drug for five days before each sampling visit. The visits will be scheduled during the early follicular phase of the menstrual cycle (approximately Days 2-5 after the first day of menses, Visit 1) when estradiol is predicted to be the lowest; and the late follicular phase (approximately Days 12-15 after the first day of the menses, Visit 2) when estradiol is predicted to be highest. After participant education, informed consent, and screening for study eligibility, participants will be evaluated at baseline.

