## 10.4 Study Sampling

At both sampling visits, the following samples will be collected in all participants:

1. Blood plasma
2. Serum

3. PBMCs
4. Rectal tissue biopsies
5. Rectal cell collection by cytobrush

10.5 Primary Endpoints:

TFVdp, FTCtp, dATP and dCTP concentrations in mixed rectal cells collected via cytobrush vs CD4+ T cells isolated from rectal tissue biopsies during the early (low estradiol) and late (high estradiol) follicular phases of the menstrual cycle

10.6 Secondary Endpoints:

1. Estradiol, progesterone and testosterone concentrations in serum
2. TFVdp, FTCtp, dATP and dCTP concentrations in peripheral blood mononuclear cells
3. TFV and FTC concentrations in plasma

Table 1 Sample collection and bioanalytical measurement

Matched Visit 1 and 2 Measurements	
Collection Matrix	Bioanalytical assay
PBMCs	TFVdp FTCtp dATP dCTP
Total rectal cells	TFVdp FTCtp dATP dCTP
Rectal CD4 cells	TFVdp FTCtp dATP dCTP
Plasma	TFV FTC
Serum	Estradiol progesterone testosterone
TFVdp=tenofovir diphosphate; FTCtp=emtricitabine triphosphate; dATP=deoxyadenosine triphosphate; dCTP=deoxycytidine triphosphate; TFV=tenofovir; FTC=emtricitabine	

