## 11.2 Subject Withdrawal

There is a low chance of participant withdrawal from the study due to the relatively short study period. If a participant does withdraw before completion of all biopsies and samples, it will be necessary to replace them in order to have a complete set of data. If a subject completes all biopsies but misses more than 1 outpatient dose it will be necessary to replace the subject in order to have a complete set of data. If a subject is unable to provide all of the serum samples because of poor vascular access or other issues it will be necessary to replace the subject in order to have a complete set of data.

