### 16.1 Statistical analysis.

*We hypothesize that PrEP nucleotide concentrations in total rectal cells obtained via cytobrush will significantly correlate with isolated CD4+ T cells regardless of estradiol exposure.* To test this hypothesis TFVdp and dATP concentrations in total rectal cells collected by cytobrush at each visit will be compared to CD4+ T cells isolated from rectal biopsies using Pearson's correlation. We expect strong correlations ( $>0.8$ ) to exist during both visits. Linear regression will be performed for log10 concentrations of total rectal cells (X) vs isolated CD4+ T cells (Y) to describe the relationship between these sampling matrices within each visit. These analyses will also be performed for FTCtp and dCTP.

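### Section 16.1 judges independence from estradiol by separate within-visit correlations and never uses the serum estradiol measured at both visits

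*Combined protocol and SAP*

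**What the plan says.** **Objective and hypothesis.** Section 9.1 sets out to assess the effect of high and low "estradiol exposure on PrEP nucleotide concentrations in different cellular populations of the lower GI tract". Section 16.1 hypothesises that cytobrush concentrations "will significantly correlate with isolated CD4+ T cells regardless of estradiol exposure".

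**How exposure is defined.** Section 10.1 schedules two visits in approximate day windows. Visit 1 falls where estradiol is predicted to be lowest, and Visit 2 in "the late follicular phase (approximately Days 12-15 after the first day of the menses, Visit 2) when estradiol is predicted to be highest". Section 10.5 carries these predictions into the primary endpoint as labels: concentrations are compared "during the early (low estradiol) and late (high estradiol) follicular phases of the menstrual cycle".

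**What is measured.** Section 10.6 lists "Estradiol, progesterone and testosterone concentrations in serum" as a secondary endpoint. Table 1 places the hormones under "Matched Visit 1 and 2 Measurements". Section 11.2 protects their completeness: if a woman is "unable to provide all of the serum samples because of poor vascular access or other issues it will be necessary to replace the subject".

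**What is analysed.** For TFVdp, dATP, FTCtp and dCTP, Section 16.1 gives Pearson's correlation at each visit and a log10 regression of CD4+ T cells on total rectal cells, "to describe the relationship between these sampling matrices within each visit". Estradiol is not a variable in Section 16.1 or 16.2. Section 9.2 has secondary objectives relating hormones to drug concentrations, but Section 16 gives no method for them.

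**The concern.** The hypothesis is about estradiol, while the analysis is about visits. The two coincide only if estradiol really differed between the visits, and the plan takes that from a prediction. Section 16.1 contains no estimate of the achieved difference and no statement of what happens to the conclusion if the difference is small.

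Two further gaps follow. First, a significant correlation at each visit does not show that the cytobrush-CD4 relationship is the same at both, and nothing in Section 16.1 compares the visits. Second, the effect of estradiol on nucleotide concentration, which is the primary objective as worded, has no planned analysis.

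Section 8 gives the purpose as deciding whether cytobrush is a valid surrogate in people taking exogenous estradiol. A reader would carry the conclusion to that setting, so its wording should rest on measured exposure.

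**Working it through.** **1. The plan's own figure.** Section 16.2 states 80% power with 10 women and r above 0.78, using the R package pwr. The text gives neither alpha nor sidedness, so I assume two-sided 5%.
- Critical r = t/√(t² + n − 2), with t(0.975, 8) = 2.306: 2.306/√(5.318 + 8) = 0.632.
- Fisher z of 0.78 with the bias term r/(2(n − 1)): 1.045 + 0.78/18 = 1.089. Fisher z of 0.632 is 0.745.
- Power = Φ((1.089 − 0.745) × √7) = Φ(0.91) = 81.9%.

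This agrees with the stated 80%. One-sided 5% gives 89.4% and does not match. Estradiol does not enter the calculation, so nothing below alters it.

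**2. Can the hypothesis be supported with no estradiol contrast?** Suppose estradiol is the same at both visits and the true correlation is the same at each. With visits independent, the chance that both are significant is the square of the single-visit power.

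| True r at each visit | Formula | Simulation (200,000 replicates) |
|---|---|---|
| 0.78 | 0.819² = 0.67 | 0.70 |
| 0.80 | 0.854² = 0.73 | 0.75 |
| 0.944 (earlier rectal fluid versus tissue figure, Section 16.2) | 0.998² = 0.996 | 0.996 |

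The same women attend both visits. Positive dependence between the two tests would raise these values, up to the single-visit power.

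**3. Do two significant correlations show the same relationship?** With n = 10 and an observed r of 0.78, the 95% interval on the Fisher scale is 1.045 ± 1.96/√7, which gives r from 0.30 to 0.95. If the true values were 0.80 at one visit and 0.50 at the other, both would still be significant in about 28% of simulated trials. A direct two-sided 5% comparison of the two correlations would detect the difference in about 18% (independent visits).

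**4. What a paired estradiol summary would deliver.** With 10 pairs, the 95% interval for the geometric mean ratio is the estimate divided and multiplied by 10^(t(0.975, 9) × SD/√10) = 10^(0.715 × SD). SD is that of the within-woman log10 ratio. It is not in the documents, so I assume a range.

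| Assumed SD | Factor |
|---|---|
| 0.2 | 1.39 |
| 0.3 | 1.64 |
| 0.4 | 1.93 |
| 0.5 | 2.28 |
| 0.6 | 2.69 |

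The interval excludes 1 when the observed ratio exceeds the factor. The only contrast in the documents is the 6-9 fold peak/trough figure in Section 14.7, for 21/7 contraceptive cycles. An observed 6-fold ratio at SD 0.3 would have an interval of 3.7 to 9.8, and at SD 0.5 of 2.6 to 13.7. A 2-fold ratio at SD 0.5 would have 0.9 to 4.6, which includes 1.

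**5. Why individual ratios are needed too.** Suppose 4 of 10 women had no change and 6 had exactly 6-fold. The geometric mean ratio is 6^0.6 = 2.9. The SD from this mixture alone is 0.778 × √(0.6 × 0.4 × 10/9) = 0.40, giving an interval of 1.5 to 5.7. With 9-fold in the six women, the ratio is 9^0.6 = 3.7 and the interval 1.7 to 8.4. Both intervals exclude 1, so only the individual values would reveal the four women without contrast.

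**The case against.** **Measured estradiol is already within the planned reporting.** It is an endpoint, it is matched by visit, women without serum are replaced, and Section 9.2 commits to relating it to nucleotide concentrations. This stands in part: the values will exist and would probably be reported. But no estimator is given for them, and nothing ties them to the primary conclusion.

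**A failed contrast is not shown to be likely.** This also stands. Section 14.7 expects 6-9 fold, and step 5 shows that a sizeable mean ratio survives even if several women show no change. However, the 6-9 fold figure comes from cited sources, applies to 21/7 users, and describes peak against trough rather than the two visit windows.

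**A stronger reading is tempting.** The windows are stated once for all cycles of 21-35 days, so a reader might infer that a calculable share of women will miss the estradiol peak at Visit 2. The documents do not support this. They give no distribution of cycle length, no ovulation timing and no number of contraceptive users. The windows are approximate, menstrual history taken at screening could guide scheduling, and the sampling figure is not shown. A visit near the peak but not on it may still have high estradiol.

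**Added models will be weak with 10 women.** True, and for that reason they should be exploratory.

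**Conclusion.** The concern holds as a gap in the analysis plan that affects interpretation. As written, two significant within-visit correlations would be read as support whatever the estradiol exposure. That outcome has about a 67-70% chance at r = 0.78 with no estradiol contrast at all, assuming two-sided 5% tests and independent visits. The primary objective also lacks an analysis relating estradiol to concentration.

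The finding rests on the text of Sections 9.1, 10.1, 10.5 and 16.1 and does not depend on the assumed SDs. The 80% power figure reproduces and is unaffected. The documents do not show that the contrast will be lost, or by how much, and they do not show that the visit labels are wrong. The text should be changed before nucleotide results are seen.

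**What to change.** Keep the Section 16.1 analyses and add the following.

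1. **Achieved contrast.** Report the paired Visit 2/Visit 1 geometric mean estradiol ratio with its 95% confidence interval, each woman's ratio, and progesterone at each visit. If the interval includes 1, word the conclusion as holding at both cycle-phase visits rather than regardless of estradiol exposure. The 6-9 fold figure in Section 14.7 is context for 21/7 users and should not serve as a threshold.
2. **Supportive repeated-measures models, each with a random woman effect.** The first takes log10 CD4+ T cell concentration on log10 cytobrush concentration, log10 measured estradiol and their interaction. It compares the cytobrush-CD4 relationship across estradiol levels. The second takes log10 nucleotide concentration on log10 estradiol by matrix, which answers the primary objective.

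Report the models as estimates with intervals, labelled exploratory, with no pass/fail test. State that 10 women give only 10 within-woman estradiol contrasts. State also that these contrasts are confounded with visit order and the second five-dose course, since Visit 2 follows both.

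A subset analysis restricted to women above some fold change is not advised. The documents supply no fold, and at r = 0.78 power falls from 82% with 10 pairs to 69% with 8 and 60% with 7.

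**Cost.** Some added text and a little more analysis, imprecise with 10 women. No new samples, visits, assays or participants.
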